6.4. Exposure

For participants in the safety population during the VC and LTS periods, descriptive statistics will be provided by treatment group for duration of treatment, average daily dose, and total dose. Duration of treatment with ruxolitinib cream or vehicle cream is defined as the number of days from Day 1 to the last record of ruxolitinib cream or vehicle cream application in the specific period.

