Table 3: Schedule of Activities: Vehicle-Controlled Period (Continued)

[figure not shown]
Visit Day (Range)	Screening	Vehicle-Controlled Treatment				Notes
	Days -28 to -1	Day 1 (Baseline)	Week 2 (± 3 d)	Week 4 (± 3 d)	Week 8*/EOT (± 3 d)	
Laboratory assessments	Blood draw for clinical laboratory tests must be performed before the in-clinic study drug application.					
Serum chemistries	X	X	X	X	X	
Hematology	X	X	X	X	X	
Serology	X*					*HIV antibody.
Pregnancy testing	X*	X	X	X	X	*Female participants of childbearing potential will have a serum test at screening and follow-up and a urine test at all other visits. A positive urine test must be confirmed by a serum test.
FSH level	X					For confirmation of nonchildbearing status of women who are postmenopausal defined as amenorrhea at least 12 months before screening.
Urinalysis	X					
PK plasma sampling (trough)			X	X	X	Time of last study drug application to be written in eCRF. Blood samples must not be drawn from the area that has been treated with study drug.

Table 4: Schedule of Activities: Long-Term Safety Extension Period

Visit Day (Range)	LTS Extension Treatment						Follow-Up	Notes
	Week 12 (±7 d)	Weeks 16, 20, and 24 (±7 d)	Weeks 28, 32, and 36 (±7 d)	Weeks 40, 44, and 48 (±7 d)	Week 52 ET/EOT (±7 d)	Unscheduled Visits		
Administrative procedures								
Contact IRT	X	X	X	X	X	X	X	
Prior/concomitant medications	X	X	X	X	X	X	X	
Apply study drug	X	X	X	X	X			1st AM application under site supervision.
Weigh/dispense or re-dispense study drug and distribute study drug diary and reminder card	X	X	X	X		X		Used tubes will be replenished and unused tubes may be re-dispensed
Collect/weigh study drug and collect/review study drug diary	X	X	X	X	X	X		
Capture start and end date of a treatment cycle	X	X	X	X	X	X	X	The start/end-date will be captured by the participant. The end date of a treatment cycle will be +3 days after lesions clear. Refer to Study Manual.
Safety assessments								
AE assessments and targeted physical examinations	X	X	X	X	X	X	X	Body systems with symptoms should be physically examined. Ad hoc photography of skin-related AEs should also occur as applicable.
Comprehensive physical examination					X			
Vital signs/body weight/height	X	X*	X	X	X*	X	X	*Height and weight at Weeks 24 and 52/EOT.
Efficacy assessments								
Evaluate %BSA affected by active AD	X	X	X	X	X	X	X	Participants may only treat up to 20% BSA.
IGA	X	X	X	X	X	X	X	

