2.3.1. Scientific Rationale for Study Design

This is a confirmatory study in a larger participant population with AD with the objective to further evaluate and confirm the prior findings with regard to the efficacy and safety of the proposed treatment regimens. The population to be studied comprises participants amenable to topical therapy of their AD, \geq 12 years of age with AD lesions covering between 3% to 20% of the total BSA, and IGA of 2 to 3.

Ruxolitinib 1.5% cream BID up to 20% BSA has been well-tolerated in participants with psoriasis, AA, AD and vitiligo clinical studies with few AEs reported and no evidence of systemic effects.

In the dose-range finding study in AD, 1.5% ruxolitinib cream BID for 8 weeks was found to be the most efficacious among investigated study arms with acceptable safety and tolerability profile (see Section [2.2.2.4.1](#) for more details). The maximum clinical effect with this treatment regimen was achieved by Week 8 and did not change significantly thereafter.

[REDACTED]

[REDACTED]

[REDACTED]

[REDACTED]

The randomized LTS period of the study will provide additional safety information when drug is used intermittently for a longer period (up to 44 weeks in total). It will also provide data about the duration of treatment effect after stopping therapy and the nature and number of disease exacerbation (flare) episodes.

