Participants who complete Week 8 assessments with no additional safety concerns will be offered to continue into the LTS period with the same treatment regimen, except for those initially on vehicle, who will be equally assigned at Week 8 to 1 of the 2 active treatment groups. At that time, the IGA score required for the participants to enter the LTS period is 0 to 4. With regard to %BSA, there is no required lower limit; participants may have BSA in the range of 0% to 20%.

In the LTS period, participants will have study visits every 4 weeks until the end of the study (52 weeks total). At those visits, AD lesions will be evaluated by the investigator to confirm if the participant still requires continuation of therapy (IGA ≥ 1) or can otherwise (re)enter the observation/no treatment cycle (IGA = 0).

During the LTS period (ie, after the Week 8 visit), participants will self-evaluate recurrence of AD and will treat areas of the skin with active AD changes (not to exceed 20% BSA). If lesions clear between study visits, participants will stop treatment applications 3 days after they have disappeared. Participants will restart treatment of their AD at the first sign of recurrence. In the event that new lesions are outside of the usual location and/or are more wide spread than at baseline, the participant is required to contact the site for approval. Approval to treat additional areas may occur via telephone during the LTS period, although the investigator, at his/her discretion, may ask the participant to return for an unscheduled visit. This is a close reflection of the clinical practice of managing AD in the outpatient setting.

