During the LTS period starting at the Week 8 visit, participants will have study visits every 4 weeks until the end of the study (52 weeks total). At those visits, AD lesions will be evaluated by the investigator to confirm whether the participant still requires continuation of therapy (IGA ≥ 1) or can otherwise (re)enter the observation/no treatment cycle (IGA = 0). At Week 8, a participant will receive a prespecified number of tubes with study medication corresponding to a lower %BSA affected (up to 5%) or higher number of tubes corresponding to their affected %BSA ($> 5\%$). This new estimate will be entered into the IRT system to calculate the number of tubes of study drug to be dispensed.

In-between study visits, the participant will self-evaluate recurrence of AD and will treat all areas identified with active AD changes (not to exceed 20% BSA). If lesions clear between study visits, participants will stop treatment applications 3 days after they have disappeared. Participants will restart treatment of their AD at the first sign of recurrence. In the event that new lesions are outside of the usual location and/or are more widespread than at baseline, the participant is required to contact the site for approval. Approval to treat additional areas may

occur via telephone during the LTS period, although the investigator, at his/her discretion, may ask the participant to return for an unscheduled visit.

Application instructions will be provided by the site study staff, and the participant will record their daily applications via a diary card given to the participants during each study visit. Refer to the Study Pharmacy Manual for participant instructions for handling study of drug. [Table 6](#) presents the study treatment information.

Table 6: Study Treatment Information

	Study Treatment 1	Study Treatment 2	Study Treatment 3
Study treatment name:	Ruxolitinib	Ruxolitinib	Vehicle
Dosage formulation:	Cream	Cream	Cream
Unit dose strength(s)/dosage level(s):	0.75%	1.5%	Not applicable

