6.5. Modifications to Treatment Regimen

Through Week 8, participants should continue to treat areas identified for treatment at baseline even if the area begins to improve. Participants who develop new AD lesions during the course of the study may treat these additional areas, with approval by the investigator, as long as the total treated BSA does not exceed 20% and there are no safety concerns. Approval to treat additional areas may occur via telephone during the VC period, although the investigator may request to have the participant come in to have an unscheduled visit, if needed.

After Week 8, for participants enrolled in the LTS period, only areas with active disease should be treated. Once the lesions are cleared, participants should continue to apply study drug for an additional 3 days on the areas of the body where lesions were last present before discontinuing the treatment. In the event that the new lesions are significantly more extensive than from the previous visit, the participant should call the study site to discuss with the investigator whether additional evaluation at the clinic is required.

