4. DATA HANDLING DEFINITIONS AND CONVENTIONS

4.1. Scheduled Study Evaluations and Study Periods

4.1.1. Day 1

Day 1 is the date that the first application of ruxolitinib cream or vehicle cream is administered to the participants in the specific period.

For randomized participants not treated with any study drug, Day 1 is defined as the day of randomization.

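### In the long-term safety (LTS) period, SAP 6.4 counts off-drug gaps between treatment cycles as duration of treatment, so the row overstates time on drug

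*SAP*

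**What the plan says.** SAP 6.4 (Exposure) applies one rule to the safety population in both the VC and LTS periods: "descriptive statistics will be provided by treatment group for duration of treatment, average daily dose, and total dose". Duration is "the number of days from Day 1 to the last record of ruxolitinib cream or vehicle cream application in the specific period". SAP 4.1.1 fixes the start of that count: "Day 1 is the date that the first application of ruxolitinib cream or vehicle cream is administered to the participants in the specific period". For the LTS, then, duration runs from the first to the last LTS application. Nothing in SAP 6.4 removes days without cream, and it gives no formula for average daily dose.

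The protocol describes LTS treatment as intermittent. Section 2.3.1 says the period is to give "additional safety information when drug is used intermittently for a longer period (up to 44 weeks in total"). Section 4.1 sets the stopping rule: "If lesions clear between study visits, participants will stop treatment applications 3 days after they have disappeared". Section 6.1 sets the restart: "Participants will restart treatment of their AD at the first sign of recurrence". Section 6.5 repeats the stopping rule: "Once the lesions are cleared, participants should continue to apply study drug for an additional 3 days on the areas of the body" where they were last present. Section 4.1 also provides for an untreated observation cycle when the IGA is 0.

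The data needed to separate treated from untreated time are collected. Protocol Table 4 has a row to "Capture start and end date of a treatment cycle", with an end date that already includes the 3 days after clearance. Protocol 6.1 has participants record daily applications on a diary card.

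SAP Appendix A plans exposure tables for the VC period, for baseline to Week 52 and for the LTS (Tables 3.1.1.1 to 3.1.1.3).

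**The concern.** A first-to-last span is a reasonable measure of treatment time when cream is applied throughout. That is the VC regimen, where areas identified at baseline are treated through Week 8. The same rule is carried into a period whose regimen is stop and restart. There it measures calendar time between two applications, yet it is called duration of treatment.

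The stake is how the long-term safety data are read. The LTS exists partly to describe safety under intermittent use. A reader of the LTS or baseline-to-Week-52 exposure table would naturally take the duration row as time on drug. Total dose shows how much cream was used, but not over how many days. Application compliance in SAP 6.5 is calculated for the VC period only, so it does not supply the missing count.

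**Working it through.** The plan states no exposure figure to reproduce, and the documents give no share of LTS days off drug. The shares below are assumptions.

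**Inputs**
- LTS length: 52 − 8 = 44 weeks, which agrees with the 44 weeks stated in the protocol; 44 × 7 = 308 days.
- VC length: 8 × 7 = 56 days, taken as all treated.
- Off-drug share of the first-to-last LTS span, g: assumed 10%, 25% or 50%.

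**What the definition counts**

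Let D be the SAP 6.4 duration, T the treated days in it and G the off-drug days between the first and last LTS application. Then D = T + G. With g = G/D, treated days are T = (1 − g) × D and the overstatement is D/T = 1/(1 − g). Off-drug days before the first or after the last LTS application lie outside D and are not counted. SAP 6.4 does not say whether one day is added to the difference in dates; this changes D by one day and does not matter here.

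**Full LTS span, D = 308**

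| Assumed g | Treated days | Overstatement |
|---|---|---|
| 10% | 0.90 × 308 = 277 | 308/277.2 = 1.11 |
| 25% | 0.75 × 308 = 231 | 308/231 = 1.33 |
| 50% | 0.50 × 308 = 154 | 308/154 = 2.00 |

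The span is shorter than 308 days if cream is first applied after LTS entry or last applied before Week 52. The ratio still depends only on g.

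**Average daily dose**

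If total dose is divided by D, the result is T/D = 1 − g of the dose per treated day: 0.90, 0.75 or 0.50. If it is divided by treated days, there is no distortion. SAP 6.4 does not say which applies.

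**Baseline to Week 52**

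With the full 56 + 308 = 364 days and the same shares, treated days are 56 + 277.2 = 333.2, 56 + 231 = 287 or 56 + 154 = 210. The ratios are 364/333.2 = 1.09, 364/287 = 1.27 and 364/210 = 1.73. SAP 6.4 defines duration within a period, so it does not settle whether this table uses one span from VC Day 1 or the sum of the two period durations. The two differ by any gap between the last VC and the first LTS application: one span includes that gap, the sum does not.

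**The case against.** The strongest reply is that the public text is incomplete where cycle analyses would sit. SAP numbering goes from 7.4.2.4 to 7.6. Appendix A lists a time-to-first-retreatment curve for the LTS (Figure 4.6) with no visible method behind it. Flare is defined in the abbreviations but is not analysed in any visible section. SAP 6 and Appendix A also refer to separate table displays and standard safety tables, which are where row labels and the average-daily-dose denominator would often be given. This stands. One might infer that the plan contains no cycle-based analysis; the documents do not support that. What remains is the SAP 6.4 definition, which is complete as written and counts the gaps. Time to first retreatment would not give treated days either.

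Second, the span is openly defined, and it fits the adverse event window in SAP 8.1, which is tied to the last application. That is a good reason to keep it. It does not make it a measure of time on drug.

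Third, the size is unknown. Protocol Table 4 marks an application of study drug at every scheduled LTS visit, while Section 4.1 allows an untreated cycle for a clear participant, and the text does not say how the two combine. If cream were applied at each visit regardless, gaps would be limited to the interval between visits, but they would still be counted. The off-drug share stays an assumption either way.

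Fourth, the consequences are limited, and this also stands. A reader might infer that LTS safety results are diluted. The adverse event summaries in SAP 8.2.2 are numbers and percentages of participants, and no visible rate uses duration as its denominator.

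**Conclusion.** The point holds as a cheap improvement to reporting. For the LTS, SAP 6.4 reports off-drug gaps between treatment cycles as treatment, so the duration row overstates time on drug. On assumed off-drug shares of 10%, 25% and 50% of a full 308-day span, the overstatement is 1.11-, 1.33- and 2.0-fold; the true share cannot be obtained from the documents.

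Two further inferences go too far. Not all off-drug LTS time is counted, only the part between the first and last application. Nor can average daily dose be called understated: that follows only if its unstated denominator is the span. Total dose, the adverse event number (%) tables, the VC period and the Week 8 analyses do not change, and no efficacy conclusion or error rate is involved.

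**What to change.** In the LTS and baseline-to-Week-52 exposure tables:

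- Keep the span, but label it calendar duration from first to last application.
- Add a row for days on treatment, counted as days with a recorded application in the diary. Where the diary is incomplete, use the recorded cycle dates, summing (end − start + 1) over cycles, and report how many participants needed this. The diary comes first because cycle dates would count days with missed applications as treated.
- Report average daily dose per treated day.
- State whether the Week-52 duration is one span or the sum of the two periods.

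Leave the VC rule unchanged.

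The cost is low: a label, one added row, a stated denominator and a short edit to SAP 6.4, all from data already collected. Appendix A lets tables and shells be modified without an SAP amendment when the nature of the analysis is not affected. The downside is that treated days rest on participant-recorded data, some of which may be incomplete.

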6.5. Study Drug Compliance

Overall compliance (%) for the application of ruxolitinib cream or vehicle cream during the VC period will be calculated for all participants in the safety population as follows:

$$\text{Overall application compliance (\%)} = 100 \times [\text{total number of nonmissing applications}] / [\text{total number of intended applications}]$$

where the total number of nonmissing applications is the total number of applications that the participant actually applied during the study.

6.6. Prior and Concomitant Medication

For participants in the ITT population during the VC period, prior medications and concomitant medications will be coded using the WHO Drug Dictionary and summarized as number and percentage of participants with prior and concomitant medications by WHO drug class and WHO drug term. For participants in the LTS period, only concomitant medications will be summarized.

Prior medications for AD will be summarized by treatment group as well as listed.

7. EFFICACY

[Appendix A](#) provides a list of planned tables, figures, and listings. Sample data displays are included in a separate document.

7.1. General Considerations

For all continuous variables, both the actual value and change and/or percentage from baseline (if available) will be analyzed.

All by-visit analyses will include the follow-up period if the data are available.

7.2. Analysis of the Primary Efficacy Parameters

For FDA submission, the primary endpoint is IGA-TS at Week 8. For EMA submission, if applicable, the primary endpoint is EASI75 at Week 8.

7.2.1. Primary Efficacy Measures

7.2.1.1. Investigator's Global Assessment

The IGA is an overall eczema severity rating on a 0 to 4 scale that will be assessed during site visits. The grades for the IGA are shown in [Table 2](#).

Table 2: Investigator's Global Assessment

Grade	Severity	Status
0	Clear	No erythema or induration/papulation, no oozing/crusting; there may be minor residual discoloration.
1	Almost clear	There may be trace faint pink erythema, with almost no induration/papulation, and no oozing/crusting.
2	Mild	There may be faint pink erythema, with mild induration/papulation and no oozing/crusting.
3	Moderate	There may be pink-red erythema with moderate induration/papulation and there may be some oozing/crusting.
4	Severe	There may be deep or bright red erythema with severe induration/papulation and with oozing/crusting.

Source: [University of Nottingham](#).

The IGA-TS is defined as an IGA score of 0 or 1 with ≥ 2 grade improvement from baseline.

7.2.1.2. Eczema Area and Severity Index Score

Atopic dermatitis will be assessed using EASI scoring system, which is a validated disease measurement for clinical studies that examines 4 areas of the body and weights them for participants of at least 8 years of age. Each of the 4 body regions is assessed separately for erythema (E), induration/papulation/edema (I), excoriations (Ex), and lichenification (L) for an average degree of severity of each sign in each region.

The disease severity strata for the EASI are as follows: 0 = clear; 0.1 to 1.0 = almost clear; 1.1 to 7.0 = mild; 7.1 to 21.0 = moderate; 21.1 to 50.0 = severe; 50.1 to 72.0 = very severe.

The categorical variable EASI75 will be equal to 1 for percentage improvement from baseline in EASI score of 75% or greater and will be equal to 0 for percentage improvement of less than 75%. EASI50 and EASI90 are defined with the same pattern.

7.2.2. Primary Efficacy Analyses

The primary analysis will be based on the ITT population in the VC period. The primary alternative hypothesis (superiority of ruxolitinib 1.5% BID or 0.75% BID compared with vehicle) will be tested using logistic regression. This model will include the treatment group (1.5% BID, 0.75% BID, and vehicle) and stratification factors (baseline IGA and region). The unadjusted p-values between each treatment group versus vehicle will be calculated based on Wald test, which will be compared with the procedure defined in Section 3.2. Exact logistic regression ([Mehta and Patel 1995](#)) will be used for all of the comparisons if any of the dose levels have an expected cell count less than 5.

Odds ratio and 95% CI in response rates (ruxolitinib cream vs vehicle) at Week 8 will also be computed. All nonresponders in the VC treatment period, as well as all participants who are missing postbaseline values, will be defined as nonresponders for the nonresponder imputation analysis.

The primary outcome will also be examined for PP population using the same model as the primary analysis.

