10.4.1. Primary Analysis

The primary analysis will be based on the intent-to-treat population. The primary alternative hypothesis (superiority of ruxolitinib 1.5% BID or 0.75% BID compared with vehicle) will be tested using logistic regression. This model will include the treatment group (1.5% BID, 0.75% BID, and vehicle) and stratification factors (baseline IGA and region). The unadjusted p-values between each treatment group versus vehicle will be calculated based on Wald test, which will be compared with 0.025 using the Bonferroni procedure. Exact logistic regression ([Mehta and Patel 1995](#)) will be used for all of the comparisons if any of the dose levels have an expected cell count less than 5.

The difference in IGA-TS rates (ruxolitinib cream vs vehicle) at Week 8 will also be computed. The 95% confidence interval for the difference will be computed based on a large-sample normal approximation with continuity correction. All nonresponders in the VC treatment period, as well as all participants who discontinue study treatment at any time before the timepoint of interest, or discontinue from the study for any reason, will be defined as nonresponders for the nonresponder imputation analysis. Sensitivity analyses, including longitudinal logistic regression with repeated measurements and multiple imputation, may be performed. In addition, a tipping point analysis will be conducted to examine the potential effects of missing data. Subgroup analysis by baseline characteristic (eg, IGA, region, and age) will be performed. Details will be provided in the Statistical Analysis Plan.

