3.3. Sample Size Considerations

Approximately 600 participants will be randomized 2:2:1 to ruxolitinib 0.75% BID, 1.5% BID, or vehicle and stratified by baseline IGA (2, 3) and region (North America or Europe). The sample size calculation is based on the Fisher exact test for the statistical comparison on the primary efficacy endpoint. The Fisher exact test is used to provide a conservative evaluation of statistical power, and it is accurate when there is a small expected number of responders in the vehicle group. Based on the results from a Phase 2, randomized, dose-ranging study (INCB 18424-206), the IGA-TS at Week 8 is assumed to be 45% and 30% for active arms (1.5% BID and 0.75% BID, respectively) versus 10% for placebo. Using a 2-sided alpha of 0.025, the sample size will have $> 95\%$ power to detect a difference between each of the 2 active treatment groups versus vehicle. In addition to provide adequate power for efficacy variables, the sample size is determined to provide an adequate database for safety evaluation.

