7.4.2.3. Categorical Efficacy Endpoints

For the following categorical parameters, summary statistics including sample size, frequency, and percentages will be presented by visits.

- Proportion of participants achieving an IGA of 0 or 1
- Proportion of participants with a \geq 2-point improvement in Itch NRS score
- Proportion of participants with a \geq 3-point improvement in Itch NRS score
- Proportion of participants with a \geq 4-point improvement in Itch NRS score
- Proportion of participants achieving EASI50
- Proportion of participants achieving EASI75

- Proportion of participants achieving EASI90
- Proportion of participants with a \geq 6-point improvement in the PROMIS Short Form (8a) – Sleep-Related Impairment 24-hour recall score
- Proportion of participants with a \geq 6-point improvement in the PROMIS Short Form (8b) – Sleep Disturbance 24-hour recall score
- Proportion of participants with a score of either 1 or 2 of PGIC
- Proportion of participants with a clinically meaningful improvement (\geq 4-point improvement) in DLQI/CDLQI

A logistic regression model with treatment and stratification factors as covariates will be fit at Week 8. The p-values between each ruxolitinib group versus vehicle will be calculated based on Wald test. Exact logistic regression will be used for all of the comparisons if any of the dose levels have an expected cell count less than 5. The NRI will be used to impute postbaseline missing values for binary outcomes based on IGA, EASI, Itch NRS, PROMIS Short Form – Sleep-Related Impairment (8a) scores, PROMIS Short Form – Sleep Disturbance (8b) scores.

For the following categorical endpoints, the number and percentage of participants will be summarized by treatment at each postbaseline visit.

- Proportion of participants in each category of EASI score
- Proportion of participants in each category of IGA score
- Proportion of participants in each category of PGIC score
- Proportion of participants in each category of POEM score
- Proportion of participants in each category of DLQI/CDLQI score
- Proportion of participants in each category of each EQ-5D dimension

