APPENDIX A. PLANNED TABLES AND FIGURES

This appendix provides a list of the planned tables, figures, and listing for the clinical study report. Standard tables will follow the conventions in the Standard Safety Tables initial version. Shells are provided for nonstandard tables. In-text tables are identical in structure and content as appendix tables, but follow a Rich Text Format.

The list of tables, figures, listings, and the shells are to be used as guideline. Modifications of the list or shells that do not otherwise affect the nature of the analysis will not warrant an amendment to the SAP.

Tables

Table No.	Title	Population
Baseline Demographic and Characteristic		
1.1.1	Analysis Populations	All
1.1.2	Summary of Participant Disposition	ITT
1.1.3	Summary of Number of Participants Enrolled by Country and Site	ITT
1.1.4	Summary of Protocol Deviations	ITT
1.2	Summary of Demographics and Baseline Characteristics	ITT
1.3	Summary of Baseline Disease Characteristics	ITT
1.4.1	Summary of Prior Medications	ITT
1.4.2	Summary of Prior Medications for Atopic Dermatitis	ITT
1.4.3.1	Summary of Concomitant Medications in VC Period	ITT
1.4.3.2	Summary of Concomitant Medications from Baseline to Week 52	ITT
1.4.3.3	Summary of Concomitant Medications in LTS Period	ITT
1.5	Summary of General Medical History	ITT
Efficacy		
IGA		
2.1.1.1	Summary and Analysis of Participants Achieving IGA-TS From Baseline to Week 52	ITT
2.1.1.2	Summary of Participants Achieving IGA-TS in LTS Period	ITT
2.1.2	Summary and Sensitivity Analysis of Participants Achieving IGA-TS at Week 8 by Tipping Point Analysis	ITT
2.1.3.1	Summary and Analysis of Participants Achieving IGA-TS From Baseline to Week 52	PP
2.1.4	Summary and Analysis of Participants Achieving IGA-TS by Baseline IGA Score From Baseline to Week 52	ITT
2.1.5	Summary and Analysis of Participants Achieving IGA-TS by Baseline EASI Score From Baseline to Week 52	ITT
2.1.6	Summary and Analysis of Participants Achieving IGA-TS by Region From Baseline to Week 52	ITT
2.1.7	Summary and Analysis of Participants Achieving IGA-TS by Age Group From Baseline to Week 52	ITT
2.1.8	Summary and Analysis of Participants Achieving IGA-TS by Sex From Baseline to Week 52	ITT
2.1.9	Summary and Analysis of Participants Achieving IGA-TS by Race From Baseline to Week 52	ITT

Table No.	Title	Population
2.1.10.1	Summary of Participants in Each Category of IGA Score From Baseline to Week 52	ITT

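### The expected-count trigger for exact logistic regression can stay silent when vehicle has no responders, leaving a Wald p near 1 in subgroup tables with a large effect

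*SAP*

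**What the plan says.** SAP 7.2.2 fits a logistic regression on the three arms and the stratification factors. P-values for each active arm against vehicle "will be calculated based on Wald test", and odds ratios with 95% CIs are also reported. Exact logistic regression "will be used for all of the comparisons if any of the dose levels have an expected cell count less than 5".

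SAP 7.4.2.3 repeats the rule for the other binary endpoints ("used for all of the comparisons if any of the dose levels have an expected cell count less than 5"), and Protocol 10.4.1 has the same condition ("if any of the dose levels have an expected cell count less than 5"). None of the three places mentions observed counts, an arm with no responders, or separation. None says whether vehicle is a dose level for this purpose, or how the expected count is obtained.

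SAP 7.2.3 lists subgroups by baseline IGA, baseline EASI, region, age, sex and race, and names no test. Appendix A, Table 2.1.4 is titled "Summary and Analysis of Participants Achieving IGA-TS by Baseline IGA Score From Baseline to Week 52", and the other IGA-TS subgroup tables follow the same pattern. Tables for which only descriptive statistics are planned have titles without the word Analysis.

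**The concern.** A logistic Wald test fails when one arm has no responders. The log odds for that arm run off to minus infinity and the standard error grows faster than the estimate, so the p-value goes to 1 however large the true difference. The remedy is an exact or penalised method, and the SAP already names an exact one.

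The difficulty is the trigger. An expected count under independence is arm size times the pooled response rate. When the active arms do well the pooled rate is high, so the expected count on vehicle looks comfortable even if the observed count is zero. The guard can therefore stay silent where active works and vehicle does not.

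The baseline IGA 2 subgroup is a natural place for this. IGA-TS needs an improvement of at least 2 grades, so a participant starting at 2 must reach 0. An age or severity table could then show p near 1 beside the largest observed difference. The sample-size text justifies the Fisher test partly by a possibly small number of vehicle responders, so sparse vehicle data were foreseen at the design stage.

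**Working it through.** **Inputs.** "Approximately 600 participants will be randomized 2:2:1 to ruxolitinib 0.75% BID, 1.5% BID, or vehicle" gives 240 / 240 / 120. "IGA-TS at Week 8 is assumed to be 45% and 30% for active arms (1.5% BID and 0.75% BID, respectively) versus 10% for placebo" (SAP 3.3). Baseline IGA 2 is capped at about 25% and adolescents are about 20% (SAP 3). With 2:2:1 kept within subgroups (an assumption), the arms are 60 / 60 / 30 and 48 / 48 / 24.

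**1. The plan's own figure.** The two-sided Fisher exact test at alpha 0.025 with 240 v 120, by full enumeration, gives power of 98.9% for 30% v 10% and above 99.9% for 45% v 10%. The stated power above 95% reproduces.

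**2. Does the trigger fire with no vehicle responders?** Expected responders = arm n × total responders / total N. Active arms are set at the planned 30% and 45%.

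| Table (vehicle, 0.75%, 1.5%) | Each active arm, three-arm table | Vehicle, three-arm table | Vehicle, pairwise (0.75%; 1.5%) |
|---|---|---|---|
| IGA 2: 0/30, 18/60, 27/60 | 60×45/150 = 18 | 30×45/150 = 9 | 30×18/90 = 6; 30×27/90 = 9 |
| Adolescents: 0/24, 14/48, 22/48 | 48×36/120 = 14.4 | 24×36/120 = 7.2 | 24×14/72 = 4.67; 24×22/72 = 7.33 |

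The IGA 2 table stays at 5 or more on every reading that uses observed margins. The adolescent table fires only on the pairwise reading, through 4.67.

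**3. What would be reported** (treatment-only fits)**.**

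| Table | Wald p (0.75%; 1.5%) | Fisher p (0.75%; 1.5%) |
|---|---|---|
| IGA 2, 0/30 | about 0.99; about 0.99 | 0.0004; 0.0000015 |
| Adolescents, 0/24 | about 0.99; about 0.99 | 0.003; 0.00002 |
| IGA 2, 1/30 | 0.017; 0.0026 | 0.0026; 0.00002 |
| Adolescents, 1/24 | 0.036; 0.005 | 0.014; 0.0003 |

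With zero responders the fit diverges (IGA 2, 1.5%: log odds ratio about 18, SE about 1,637), so the printed p depends on the software's stopping rule; another fit gave 0.999. With one responder Wald is conservative but finite.

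**4. How likely is zero on vehicle?** P = (1 − rate)^n.

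| Vehicle n | 10% (planned) | 5% (assumed) |
|---|---|---|
| 120 (whole trial) | 0.000003 | 0.2% |
| 30 (IGA 2) | 4.2% | 21% |
| 24 (adolescents) | 8.0% | 29% |

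**5. How often would a reading that counts vehicle catch it?** Given zero vehicle responders:

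- Adolescents, pairwise: 24×x/72 < 5 means x ≤ 14 responders of 48 on an active arm. At the planned rates this happens in about 53% of tables.
- IGA 2 with all rates halved (22.5% and 15% on active, 5% on vehicle; an assumption), three-arm: 30×T/150 < 5 means T ≤ 24 responders in total, about 69% of tables.
- The same, pairwise: 30×x/90 < 5 means x ≤ 14 of 60 on either active arm, about 99% of tables.

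**The case against.** The strongest reply is that the rule is less blind than it looks. SAP 3.2 uses dose level for the whole family of comparisons of one dose with vehicle, so vehicle cells may be meant to count, pair by pair. On that reading about half of the adolescent tables with no vehicle responders already go to the exact method. It can also be said that lowering only the vehicle rate in the IGA 2 subgroup is lopsided: reaching IGA 0 is harder on active cream too, and with all rates halved the rule catches most of these tables once vehicle counts. Both arguments stand and limit the reach of the point. They do not remove it. The text does not state the pairwise reading, and the IGA 2 example at the planned active rates passes silently on that reading as well. If expected meant sample size times planning rate with vehicle included (30 × 0.10 = 3), the rule would fire, but the documents do not say so.

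It is also fair that SAP 7.2.3 names no model and that Appendix A calls its lists and shells a guideline. Use of the Wald model in subgroups is inferred from the table titles.

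A reader might infer three stronger things that the documents do not support:

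- *One vehicle responder also gives p near 1.* It does not; the Wald p-values in the examples run from 0.0026 to 0.036.
- *Low-rate endpoints such as EASI90 are equally exposed.* Appendix A tabulates EASI90 only in the whole ITT population, with about 120 on vehicle, where zero responders has a 0.2% chance at a 5% rate.
- *The primary or alpha-controlled result is at risk.* About 120 × 0.10 = 12 vehicle responders are expected for IGA-TS, and subgroups carry no alpha.

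**Conclusion.** The point holds for the subgroup tables, as a gap in a stated rule. A trigger built on expected counts does not detect separation, and in a plausible IGA 2 table it leaves a Wald p of about 0.99 or higher and an unbounded odds ratio where Fisher gives 0.0004 and 0.0000015.

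The chance of zero vehicle responders is about 4% (IGA 2) or 8% (adolescents) at the planned rate, and 21% or 29% at an assumed 5%. These are upper limits on the chance of the misleading output, because the existing trigger catches some cases if vehicle counts pairwise or if active response is also lower.

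This rests on 2:2:1 allocation within subgroups, IGA 2 enrolment at its cap, use of the 7.2.2 model in subgroups, and fits without the stratification factors. The overall primary test is practically unaffected and needs no change.

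**What to change.** For the SAP 7.2.3 subgroup tables and the 7.4.2.3 endpoints:

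1. Name the model used in subgroups, and state that vehicle cells count toward the expected-count rule.
2. Add that whenever any compared arm, vehicle included, has zero observed responders or zero nonresponders, the p-value comes from exact logistic regression and the odds ratio and CI from Firth penalised likelihood.

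The first step alone would not repair the IGA 2 example, where the vehicle expected counts are 6 or more. Exact regression alone would correct the p-value but leave one confidence limit infinite, hence Firth for the estimate.

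Leave the primary analysis in 7.2.2 as planned. A broader trigger, such as fewer than 5 observed responders in any arm, would go too far. At a 10% vehicle rate it would fire in about 82% (n=30) to 91% (n=24) of these subgroup tables. If applied to 7.2.2, it would switch the primary test in about 28% of trials at a 5% vehicle rate.

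The cost is a short addition to the SAP and a few extra runs. The drawback is that in those sparse tables the p-value and the interval come from different methods and may not agree exactly; a footnote can say so.
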